Concomitant Medication Review (including immunosuppressants) ⁹	X	X ^P		X ^P	X	X ^P			X ^P	X	X ^P		X	X
Health Economic Assessment (HEA)	X	X ^P		X ^P		X ^P			X ^P		X ^P		X	X
Clinical Laboratories ¹⁰	X	X ^P	X	X ^P	X	X ^P	X		X ^P	X	X ^P	X		X
Urinalysis, with Microscopic Evaluation	X	X ^P	X	X ^P	X	X ^P	X		X ^P	X	X ^P	X		X
Urine:Protein Creatinine Ratio	X	X ^P	X	X ^P	X	X ^P	X		X ^P	X	X ^P	X		X
Pregnancy Test (females) ¹¹	X	X ^P		X ^P		X ^P			X ^P		X ^P		X	X
CMV Serologies ¹²	X													
Adverse Event and SAE Review ¹³	X	X ^P		X ^P	X	X ^P			X ^P	X	X ^P		X	X
Transplant Information ^{14, 15}		X												
Randomization ¹		X ^P												
CMV Plasma Viral Load Testing (see Table 1a) ^{16, 17, 24}									Every 2 Weeks →			Monthly →		
CMV Genotypic Resistance Testing, when applicable ^{18, 24}			→											
Immunology Lab ^{19, 24}		X ^P			X	X ^P				X	X ^P			X
Pharmacogenomics (PGx) – (Optional) ^{20, 24}		X ^P												
Study Drug injection ²¹		X		X		X			X		X			
Local & Systemic Reactogenicity Assessment ²²		X		X		X			X		X			
Patient and Graft Survival														X

P = procedure should be completed prior to dosing * = Visit procedures may be performed by Home Health Care (HHC)

Table 1a: Plasma Viral Load Schedule

	Every Other Week							Monthly							
	Day 100*	Day 114*	Day 128*	Day 142*	Day 156*	Day 170*	Day 184	Day 198*	Day 230*	Day 260	Day 290*	Day 320*	Day 350*	Day 380*	Day 395
CMV Visit Window (days)	+/-3	+/-3	+/-3	+/-3	+/-3	+/-3	+/-5	+/-5	+/-5	+/-5	+/-5	+/-5	+/-5	+/-5	+14/-5
CMV Window							Day 179-189	Day 193-203		Day 255-267					
Overlap with Regular Visit†							Days 179-185	Days 191-197		Days 260-267					Days 395-409
May draw with Visit:	Visit 7*						Visit 10	Visit 11*		Visit 12					Visit 13
CMV Plasma Viral Load Testing ^{16, 17, 24}	X	X	X	X	X	X	X ^p	X	X	X	X	X	X	X	X

* = Visit procedures may be performed by Home Health Care (HHC). Viral load blood draws may be combined with Visits 10, 11 12 & 13 at the investigator site when they are scheduled to coincide within each visit’s windows .

† Days in Study Schedule when CMV and Regular Visit can be performed together per Protocol. The overlap used assumes the visits are done exactly on the specified visit day from Transplant. If +/- window is used for a dosing visit, the corresponding follow up visit should take place within the 14 days +/-3 from the date of the Study Drug dose. Visits 10 & 11 must be at least 7 days apart.

Tables 1 and 2 Footnotes:

1. Screening may be done from Day -14 up to Randomization, Day 30. Screening and Randomization can take place on the same day as long as Clinical Labs are drawn and results are available on the day of Randomization. If Screening is done > 3 days prior to Randomization, Clinical Labs, urinalysis and urine protein: creatinine ratio must be repeated and available prior to Randomization. Subjects may be rescreened due to rescheduling of transplant surgery provided the screening procedures are repeated and fall within the -14 day to + 30-day window relative to the Day of Transplant. First study drug dosing must take place within 24 hours of Randomization.
2. The date of transplant (day of skin closure) defines Day 0 and all visit days are relative to Day 0.
3. Subjects are to receive prophylactic valganciclovir or ganciclovir starting within 10 days post transplant through the Day of Randomization to prevent CMV disease. (The subject can miss up to two doses of valganciclovir or ganciclovir during this time period for any reason). Valganciclovir or ganciclovir dose is to be given per the package insert. The subject will then continue to receive CMV-specific AVP until 100 days post transplant. Subjects can have CMV-specific AVP interrupted, dose adjusted or replaced by other CMV-specific AVP per standard of care after the Day Randomization if renal function is compromised, there are toxicities related to the administration of the AVP, or for any other medically indicated reason.
4. Informed consent must be obtained prior to the performance of any study-related procedure.
5. Subjects will be assigned a subject number for use throughout the study at the Screening Visit via the Interactive Response Technology (IRT) system.
6. The EQ-5D, Kidney Transplant Questionnaire (KTQ) and the SF-12 v2, should be completed by the subject prior to any other study assessments or visit procedures. Subjects should complete these assessments in the following order: EQ-5D first, KTQ second, SF-12 last. For all three patient-reported outcome measures, i.e. EQ-5D, KTQ, SF-12, the answers must come from the subject. If the subject is unable to fill out the questionnaire, the assessment should not be performed. If the subject is unable to answer an individual question, the rest of the questionnaire should still be completed.
7. Medical history must include demographics, (age, gender, race), diagnosis for renal failure, length of time on dialysis, history of prior kidney transplant, and diabetes.
8. A complete physical examination (PE) will be conducted at the Screening, Baseline and the Study Completion/Day 395 Visit (V13). At all other visits where a PE is performed (Visits 4, 6, 8, 10 and 12); symptom-directed physical examinations may be done. The evaluations conducted at each visit are to be performed by the Investigator or qualified medical personnel who routinely perform these evaluations in this patient population. Vital signs will be collected immediately prior to Study Drug injection, at 15 minutes and 60 minutes post Study Drug injection. Vital signs include blood pressure, pulse rate, respiratory rate and temperature. Height will be collected at the Screening Visit only. Weight will be collected at V1, V2 and at Study Completion/Day 395 (Visit 13). If Screening is done > 3 days prior to Randomization, the PE must be repeated at Randomization.
9. All concomitant medications and therapies administered from 14 days prior to transplant through the Study Completion Visit (Day 395/Visit 13) will be collected on the eCRF. Medications used for anesthesia during the transplant surgery will not be recorded.
10. Clinical laboratory samples will be drawn at Screening (Visit 1), before each Study Drug injection, at each follow-up time point for the injections, and at the last study visit. Clinical labs will be performed by a local laboratory and will include hematology, biochemistry, including a hepatic profile, urinalysis with microscopic evaluation and urine protein: creatinine ratio. Screening clinical labs may be re drawn once if initial results would preclude Randomization and the Investigator feels out of range results were transient. Results will be entered into the eCRF. Safety labs (hematology, biochemistry, hepatic profile, urine protein: creatinine ratio and urinalysis) drawn by Home Health Care for Investigator sites utilizing this service will be analyzed by the Central Laboratory.

11. For all females of childbearing potential, a urine pregnancy test will be performed at Screening, prior to each dose, at Visit 10, 12, and at the Study Completion/Day 395 Visit (Visit 13). All pregnancy tests will be done locally. For subjects who receive mycophenolate mofetil (MMF), additional pregnancy testing should be done in accordance with local requirements.
12. CMV serologies must have been performed within 8 weeks prior to transplant. If CMV serostatus is not available from this time period, CMV serostatus may be assessed at the Screening Visit with results available prior to Randomization.
13. AEs and SAEs will be collected from time of signing of informed consent through one year post Study Drug injection [Study Completion Day 395 Visit (Visit 13)]. AEs should be recorded as a change in medical status or medical history, from the time of signing of the informed consent until the first dose of study drug. SAEs from the time of signing the informed consent will be recorded on the SAE worksheet and reported per Section 5.5.6. AEs reported after the first dose will be reported on the AE eCRF. Note: The transplant surgery that occurs on Day 0 is not considered an AE or an SAE.
14. Transplant information includes type of transplant (Living Related Donor, Living Unrelated Donor, or Deceased Donor).
15. Donor information includes donor demographics (age, gender, race), viral serologies (CMV [required], HBV, HCV, EBV, [if available]; and HCV PCR RNA [if available]), ABO blood group and HLA typing. Recipient information includes ABO blood group, HLA typing, HLA cross match at time of transplant (as determined by the site's standard method of determination), and viral serologies (CMV [required], HBV, HCV and EBV [if available], and HCV PCR RNA [if available]).
16. Plasma viral load by the central laboratory will be routinely monitored every other week (+/-3 days) from Day 100 through Day 200, then monthly (+/- 5 days) until end of study. Plasma viral load by central and local laboratory will also be assessed for cause in case of suspect CMV disease and at least once a week by Central lab from initiation of CMV-specific AVT until the course is completed. For cause CMV viral loads should be performed at a local lab approved by Astellas as Central lab viral load results may not be available in a timely manner to guide treatment decisions.
17. Plasma viral load assessment results performed by the local laboratory will be reported on the eCRF. Local CMV plasma viral load testing may be performed only at a local laboratory approved by the Sponsor.
18. A plasma sample will be drawn and sent to the central lab and results will be reported for CMV genotypic resistance when there is viremia without a reduction in viral load after two weeks of treatment with valganciclovir and/or ganciclovir, or when clinical signs and symptoms have not improved two weeks after initiating or increasing valganciclovir and/or ganciclovir for CMV viremia or disease or any time resistance to any CMV-specific AVT is suspected by the Investigator.
19. Immunogenicity laboratories include collection of blood for the gB antibody and pp65 T-cell assays. Samples should be drawn at Visits 2, 5, 6, 9, 10 and 13. Visits 2, 6 and 10 are Study Drug injection visits and blood sampling will be collected prior to the Study Drug injection. Samples for T-cell assays will not be collected if the Absolute Lymphocyte Count (ALC) is known to be $\leq 500 \text{ mm}^3$ by local or central laboratory measurement.
20. Subjects who consent to participate in the PGx sub study will have a whole blood sample collected during the Baseline Visit (Visit 2), after Randomization but prior to the first Study Drug injection.
21. A Study Drug injection should not be given if the subject 1) has been on an anticoagulant within 5 half-lives prior to the injection (Low dose anticoagulants that are used for prevention of deep vein thrombosis are allowed) or 2) has a Temperature $\geq 100.4^\circ \text{ F}$ or 38° C (per NCI Grade 1).
22. Local reactogenicity and symptoms of systemic reactogenicity will be evaluated one hour after each injection and then for seven days after each injection by subject reporting via diary. After injection in the clinic, the subject must be in direct view of the clinic staff for 15 minutes following each injection, then remain in the clinic area for an additional 45 minutes for evaluation of local and systemic reactogenicity. Vital signs, including temperature, pulse, respiration and blood pressure will be collected just prior to injection, 15 minutes post Study Drug injection and at one hour post Study Drug injection. Using the pre-injection vital signs as baseline, if a post Study Drug injection vital sign meets Grade 1-4 criteria per Appendix 5, they are to be repeated and confirmed within 5 minutes of the first assessment.

23. The Study Completion/Day 395 Visit (Visit 13) must occur on Day 395 up through +14 days (between Day 395 to 379). For a subject who prematurely withdraws from the study (discontinues treatment with no continued follow-up), the Study Completion Visit should be completed within 14 days of study withdrawal.
24. Specimen drawn and sent to the Central Laboratory.
25. If a Study Drug dose is missed, the 14 day follow up clinical laboratory samples for hematology, biochemistry, urinalysis and urine protein: creatinine ratio and hepatic profile should not be collected. Scheduled Immunogenicity Labs (Visit 5 & 9) must still be collected.

Table 2: Schedule of Assessments – Long-term Follow-up Period

Month	18	30	42	54	66
Year (relative to first Study Drug)	1.5	2.5	3.5	4.5	5.5
Window (months)	± 1	± 1.5	± 1.5	± 1.5	± 1.5
Mortality, including primary cause of death and date	X	X	X	X	X
Development of any new malignancies	X	X	X	X	X
Development of infection requiring hospitalization or resulting in death	X	X	X	X	X
Erythema and/or induration at sites of immunizations	X	X	X	X	X
Graft Survival	X	X	X	X	X
Creatinine*	X	X	X	X	X

Subjects will be contacted by telephone at 6 months after Day 395, then annually, for the next 4 years for long-term safety related to the DNA vaccine. Items are to be assessed by questionnaire and via retrospective chart review of available medical records.

During the long-term follow-up period, if an SAE is identified and deemed possibly or probably related to the study medication, an SAE report on the SAE worksheet must be sent to the sponsor per Section 5.5.6.

*Creatinine values will be recorded if they have been collected within 3 months prior to the follow-up telephone contact and are included in the subject’s available medical records.

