- Viral load area under the curve (AUC), as a measure of “cumulative viral load” through one year post first Study Drug injection.
- Number of episodes of adjudicated CMV-associated disease, including CMV syndrome and CMV tissue-invasive disease, through one year post first Study Drug injection.
- Number of episodes of viral resistance to ganciclovir or valganciclovir through one year post first Study Drug injection as determined by a central laboratory assay.
- Incidence of biopsy-proven (T or B cell) rejection (BPAR) (Banff 2007 Grade ≥ 1) through one year post first Study Drug injection.
- Estimated glomerular filtration rate (eGFR) at the last study visit, calculated using the 4 variable Modification of Diet in Renal Disease (MDRD) formula.

- Incidence of clinically treated acute graft rejection through one year post first Study Drug injection.
- Patient-reported outcomes through one year post first Study Drug injection:
 - EuroQol-5 dimensions 5 levels (EQ-5D)
 - Kidney Transplant Questionnaire (KTQ)
 - Short Form Health Survey version 2 (SF-12v2)
- Healthcare resource utilization through one year post first Study Drug injection:
 - Resource use will be collected including the following: hospitalizations recorded as number of days in the Intensive Care Unit, Step-down Unit, and general medical ward, (including emergency room visits greater than 24 hours), also non -protocol -related physician visits and emergency room visits of less than 24 hours.

Immunogenicity Variables

- T-cell responses to pp65 through one year post first Study Drug injection.
- gB-specific antibody levels through one year post first Study Drug injection.

Safety Assessments

- Vital signs
- Adverse events using the National Institutes of Health Common Terminology Criteria for Adverse Events (NCI-CTCAE) v. 4.03 grading scale
- Local reactogenicity signs and symptoms using both the NCI-CTCAE v. 4.03 grading scale and the protocol-specified reactogenicity scale
- Systemic reactogenicity signs and symptoms using both the NCI-CTCAE v. 4.03 grading scale and the protocol-specified reactogenicity scale
- Clinical laboratory assessments as defined in Appendices
- Physical examination

Statistical Methods:

Sample Size Justification:

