7 STATISTICAL METHODOLOGY

A Statistical Analysis Plan (SAP) will be written by the responsible biostatistician of APGD to provide details of the analysis, along with specifications for tables, listings and figures to be produced. The SAP will be finalized before the database lock at the latest. Any changes from the analyses planned in SAP will be justified in the Clinical Study Report (CSR).

Prior to database lock, a final review of data and tables, listings and forms (TLFs) meeting will be held to allow a review of the clinical trial data and to verify the data that will be used for analysis set classification. If required, consequences for the statistical analysis will be discussed and documented. A meeting to determine analysis set classifications will also be held prior to database lock.

In general, all data will be summarized with descriptive statistics (number of subjects, mean, standard deviation, minimum, median and maximum) for continuous endpoints, and frequency and percentage for categorical endpoints.

Unless specifically stated otherwise, all efficacy comparisons will be tested at 1-sided 0.05 level and safety comparisons will be tested at 2-sided 0.05 level. Confidence intervals for efficacy estimates, if provided, will be constructed at 90% level.

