12.11 Appendix 11: Common Serious Adverse Events

The following is a list of serious adverse events that the Sponsor considers to be associated with the disease state being studied. **The list does NOT change your reporting obligations or prevent the need to report an adverse event meeting the definition of an SAE as detailed in Section 5.5.3 Definition of Serious Adverse Event (SAE).** The purpose of this list is to alert you that some events reported as SAEs may not require expedited reporting to the regulatory authorities based on the classification of “common serious adverse events”. You are required to follow the requirements detailed in Section 5.5.6 Reporting of Serious Adverse Events (SAE).

For IND safety reporting, single occurrences of the following events may be excluded from expedited reporting to the FDA. If aggregate analysis of these events indicates that they occur more frequently with Study Drug, an expedited IND safety report may be submitted to the FDA.

- Kidney transplant rejection
- Kidney allograft loss
- Blood creatinine increased
- Diabetes mellitus
- Hyperglycemia
- Increase blood glucose

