7 STATISTICAL METHODOLOGY

7.1 General Considerations

All statistical analyses and summary information will be generated according to this analysis plan and any deviations from this plan will be documented in the clinical study report. Any numerical rounding should be performed at the end of calculations. The p-values will be displayed with 3 decimal places. Statistical significance will be determined prior to rounding the p-value.

For continuous variables, descriptive statistics will include the number of subjects (n), mean, standard deviation, median, minimum and maximum. Frequencies and percentages will be displayed for categorical data. Percentages by categories will be based on the number of subjects with no missing data thus the percentages will add up to 100%. Baseline will be the last non-missing value on or prior to first study drug unless otherwise specified.

All efficacy comparisons will be tested at the 1-sided 0.05 significance level. Confidence intervals for efficacy estimates, if provided, will be constructed at 2-sided 90% level.

All data processing, summarization, and analyses will be performed using SAS® Version 9.1.3 or higher on Unix.

This SAP includes the data analysis for the primary study period (ie, 1-year post first study drug injection) which is defined as data collected through day 380 (=365+14+1 day). Certain data summary will consider analysis window as specified in each section. The long-term follow-up period is not covered by this SAP and will be managed in a separate SAP.

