7.4 Analysis of Efficacy

7.4.1 Analysis of Primary Endpoint

7.4.1.1 Primary Analysis of Primary Efficacy Endpoint

The primary efficacy endpoint is the proportion of subjects with CMV viremia which is defined as plasma viral load ≥ 1000 IU/mL assessed by central assay through one year post first Study Drug injection. CMV viral load tests are scheduled once every 2 weeks for the first 8 tests starting 100 days from transplant and subsequently once per month for 7 more tests. In addition, a subject may have unscheduled tests (suspect CMV syndrome or CMV tissue-invasive disease) by the local laboratory so that the subject can be treated promptly with antiviral therapy (AVT) if needed. Everytime a local laboratory is performed, the sample should also be sent to the central laboratory for assessment. The CMV viral load collected from the central laboratory after first injection (Day 1) through day 380 ($=365+14+1$) that were collected as scheduled or unscheduled assessments will be utilized.

A patient who discontinue the study without a positive CMV viral load will be imputed as having a CMV viremia. A patient who has more than one time with viral load ≥ 1000 IU/mL by central assay will be counted once in this summary. Any unscheduled central laboratory values within the window will be included.

A Cochran-Mantel-Haenszel (CMH) test at the 1-sided 5% level stratified by use of anti-thymocyte globulin (ATG) and by receipt of a kidney from a living or deceased donor will be used to analyze the primary endpoint of CMV incidence rate.

The null and alternative hypotheses for this comparison are:

H0: Common Odds Ratio = 1.

H1: Common Odds Ratio < 1.

The odds ratio is defined as the ratio of odds of viremia in the ASP0113 group to that in the placebo group. The 1-sided p-value with the 2-sided exact 90% confidence interval for the

common odds ratio will be calculated (in SAS specifying the comor option in the exact statement of proc freq).

The primary analysis will be conducted for the FAS population.

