7.4.3 Analysis of Exploratory Endpoints

The analyses of all exploratory variables defined in Section [6.1.3](#) will be performed on the FAS. Each of these variables will be summarized by treatment. If the endpoint is measured at different visits, the variable will be summarized by treatment at each visit and at Final Visit unless stated specifically otherwise.

Comparisons between treatment groups for the following binary variables will be tested using the exact CMH method as described in Section [7.4.1.1](#)

- viral resistance to ganciclovir or valganciclovir
- biopsy-proven acute rejection (BPAR)
- clinically treated acute graft rejection

Viral resistance to ganciclovir or valganciclovir is confirmed by central laboratory. Biopsy proven acute rejection (BPAR) is captured in the CRFs. For acute antibody mediated

rejection with Banff grade ≥ 1 or for T-cell mediated rejection with grade $\geq 1a$ BPAR will be “yes”. Clinically treated acute graft rejection will be from the CRF.

The time to the first adjudicated CMV disease, including CMV syndrome and CMV tissue-invasive disease will be analyzed using the same method as described in the third sensitivity analysis in Section [7.4.1.2](#)

The following count variables may be affected by duration of follow-up which is the time of last assessment from first injection plus 1. Therefore, each of the variable will be compared between treatments using Poisson regression with treatment and randomization stratum as factors offset by follow-up time. The risk ratio, 1-sided 5% p value and the 90% confidence interval for the risk ratio will be presented.

- Number of opportunistic infections other than CMV
- Number of episodes of CMV viral load of ≥ 1000 IU/mL by central assay
- Number of episodes of adjudicated CMV-associated disease, including CMV syndrome and CMV tissue-invasive disease

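### Acute rejection is compared between arms only as an exploratory efficacy endpoint: one-sided for benefit, on the FAS, with no interval on the safety set and no statement that an excess will be looked for

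*Protocol*

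**What the plan says.** Under Exploratory Efficacy the protocol synopsis lists "Incidence of biopsy-proven (T or B cell) rejection (BPAR) (Banff 2007 Grade ≥ 1) through one year post first Study Drug injection" and "Incidence of clinically treated acute graft rejection through one year post first Study Drug injection". Neither is among the safety variables (Protocol 2.3.5 and 5.4, SAP 6.2) or the adverse events of special interest (Protocol 5.5.2, SAP 7.5.2).

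SAP 7.4.3 covers both endpoints: "Comparisons between treatment groups for the following binary variables will be tested using the exact CMH method", with a reference to SAP 7.4.1.1. That section states "H1: Common Odds Ratio < 1", where the odds ratio is ASP0113 over placebo. It also specifies a one-sided p-value and a two-sided exact 90% interval for the common odds ratio. SAP 7.1 adds: "All efficacy comparisons will be tested at the 1-sided 0.05 significance level". Exploratory endpoints are analysed on the FAS.

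Protocol section 7 separates the two kinds of comparison: "all efficacy comparisons will be tested at 1-sided 0.05 level and safety comparisons will be tested at 2-sided 0.05 level". SAP 7.5 names no test and no interval for any adverse event. It gives counts and percentages on the safety set (SAF), by system organ class and preferred term.

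The FAS (SAP 5.1) needs at least one dose and at least one post-dose central viral load within one year of the first injection. The SAF (SAP 5.2) needs only one dose and is analysed by the drug received first. Table 1a starts routine central viral loads at Day 100. Doses are scheduled on Days 30, 60, 90, 120 and 180.

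**The concern.** Safety is the trial's second objective, and the vaccine is designed to stimulate humoral and cell-mediated immunity in people carrying an allograft (Protocol 1.1). Rejection is an outcome for which a reader will want to know about a difference in either direction. The plan files it under efficacy, and three things follow. The p-value looks only for a reduction. The two-sided 0.05 standard for safety comparisons never applies to it. The population depends on having a central viral load, which has nothing to do with rejection.

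At stake is how an excess would be read. If the clinical study report gives the one-sided p-value prominence, more rejection on ASP0113 appears as no significant reduction. If subjects who leave early are also those with early rejection, they drop out of the only comparison made.

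**Working it through.** **Plan's own figure.** Neither document gives a rejection rate or a power for rejection. The one sample-size figure is for viremia: 46% versus 25%, one-sided 5%, 80% power, 64 per arm.

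n = [1.645·√(2·0.355·0.645) + 0.842·√(0.46·0.54 + 0.25·0.75)]² / 0.21² = (1.113 + 0.556)² / 0.0441 ≈ 63.2, rounded up to 64.

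This reproduces, but says nothing about rejection. All rejection rates below are assumptions, with 70 per arm and no stratification.

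**One data set.** Take 18/70 on ASP0113 and 7/70 on placebo (25.7% versus 10.0%), 25 events in all. Conditional on the 25 events, with no effect the ASP0113 count X is hypergeometric.
- Planned one-sided p-value, P(X ≤ 18) = 0.996: no signal.
- Two-sided exact p-value = 0.026. The arms are equal, so the harm tail P(X ≥ 18) is half of that, 0.013.
- Exact 90% interval for the odds ratio = 1.29 to 7.95: excludes 1 on the side of harm.
- Risk difference = 0.257 − 0.100 = 0.157. SE = √(0.257·0.743/70 + 0.10·0.90/70) = 0.0634. The 95% interval is 0.157 ± 1.96·0.0634, about +3 to +28 percentage points.

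The p-value and the interval come from the same planned method. The first is silent and the second is not.

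**Over repeated trials.** Exact enumeration of two binomials, 70 per arm:

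| Placebo vs ASP0113 (assumed) | One-sided benefit test significant | Lower limit of exact 90% interval above 1 | Two-sided 5% score test shows harm |
|---|---|---|---|
| 10% vs 20% | 0.02% | 42% | 38% |
| 10% vs 25% | below 0.02% | 69% | 66% |
| 15% vs 35% | below 0.02% | 83% | 80% |

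A lower 90% limit above 1 is a one-sided 5% test for harm, so it finds an excess slightly more often than the two-sided 5% test.

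**Limit set by size.** For a doubling of rejection, a two-sided 5% test at 70 per arm has power of about 20% (from 5%), 38% (from 10%), 58% (from 15%) and 75% (from 20%). For 80% power the numbers needed per arm are 435, 199, 121 and 82.

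**Population.** The first routine central draw (Day 100) comes after three of the five scheduled doses. A subject dosed at Day 30 who leaves before Day 100 enters the FAS only through a for-cause central draw or one taken at an early-termination visit. Without either, the subject is in the SAF and absent from the rejection comparison. The documents give no number for such subjects. The planned allowance for drop-out is 70 − 64 = 6 per arm. The SAP describes it as randomized but not evaluable, so it may include subjects never dosed. It is a planning figure, not an estimate.

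**The case against.** The strongest reply is that the planned output already shows harm. SAP 7.4.3 refers to the method of 7.4.1.1, and the two-sided exact 90% interval is part of that method. This stands. A reader might infer from the one-sided p-value that the planned analysis would flag an excess in almost no trial. The documents do not support that, because the table above shows the interval doing so about as often as a two-sided test. What remains is that 7.4.3 speaks of testing these variables but spells out an interval only for the count endpoints, SAP 7.1 gives efficacy intervals only if provided, and nothing says to read this one for harm.

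Rejection is also not ignored as a safety event. If reported as an adverse event it enters the SAF tables by arm, including serious events and severity. Graft survival and eGFR change are compared between arms. This too stands, but the adverse-event tables carry no between-arm estimate, and graft survival and eGFR are also analysed on the FAS.

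Protocol Appendix 11 invites another strong reading: that single cases of rejection are excused from expedited FDA reporting because an aggregate analysis will catch an excess. The text does not say so. Its reason is that these events are associated with the disease state. Investigators must still report every case, and Protocol 5.5.8 has the sponsor monitor frequency. The clause beginning "If aggregate analysis of these events indicates that they occur more frequently with Study Drug" concerns IND safety reporting, so its absence from SAP 7.5 is not a contradiction.

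No passage says the vaccine may raise rejection. Protocol 1.1 anticipates only a reduction, so the harm direction is an inference from the mechanism. Nor can one conclude that the DMC lacks a rejection table: its safety analysis plan is in the DMC Charter, which is not among the documents.

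Finally, SAP 7.5 is descriptive for every adverse event, so asking for an interval on one of them is partly judgement. And subjects who stop treatment, including for graft failure, are to stay in follow-up, so the loss from the FAS is confined to those who leave the study before any central draw.

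**Conclusion.** The point holds as one of population and presentation. The only comparative rejection analysis is one-sided for benefit and excludes dosed subjects without a post-dose central viral load. The p-value cannot signal an increase. The accompanying 90% odds-ratio interval can, but its use for that purpose is unstated and it inherits the FAS restriction. The safety section offers counts without an interval.

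The size is modest. The information in the interval is comparable with a two-sided test, and at 70 per arm even a doubling from 10% to 20% would be found in only about 38% of trials. How many subjects fall outside the FAS is unknown. These figures rest on assumed rejection rates, 70 per arm and unstratified calculations; the stratified analysis would differ slightly.

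**What to change.** Keep the exploratory efficacy test as it is. Add to SAP 7.5 one table on the SAF, by drug received, from first injection through Day 380 (the SAP's primary study period). It should give number and percent of subjects with BPAR and with clinically treated rejection in each arm, and a two-sided 95% interval for the risk difference stratified by ATG use and donor type. That matches Protocol section 7, where "safety comparisons will be tested at 2-sided 0.05 level". Add one sentence that an excess of rejection will be judged from this interval and not from the one-sided efficacy p-value.

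The cost is SAP wording and one table from data already on the case report form. The downside is one more unadjusted safety comparison, with limited power. An interval that includes zero should not be reported as evidence of no increase.
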